9.3 Analysis populations

Randomized Population: The randomized population will include all subjects who were randomized to treatment. Baseline (screening) variables and demographic characteristics will be summarized for this population.

Intent-to-Treat Population (ITT): The ITT population will include all randomized subjects who have received at least one dose (2 drops) of study medication. This population will be the primary population for the efficacy analyses and all efficacy variables will be summarized using this set of subjects. The ITT population will include subjects as randomized.

Per-protocol population (PP): The PP population is a subset of the ITT population, which will include those subjects (and their visits) who do not have major protocol violations likely to seriously affect the primary outcome of the study as judged by a masked evaluation prior to the unmasking of the study treatment. This population will be the secondary population for efficacy

analyses and all efficacy variables will be summarized using this set of subjects. If the PP and ITT populations are exactly the same and there are no missing data, then additional efficacy analyses on the PP population will not be performed. The PP population will include subjects as treated.

Safety Population: The safety population will include all randomized subjects who have received at least one dose (2 drops) of study medication. This population will be used to summarize the safety variables and will summarize subjects as treated.

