### **2.2 Description of Trial Design**

This is a Phase 3, randomized, placebo-controlled, double-masked, parallel-group design study of safety and anesthetic efficacy of AG-920 topical drop versus placebo in healthy subjects. The study will evaluate the safety and anesthetic efficacy following one dose of Articaine Sterile Topical Ophthalmic Solution (AG-920), in comparison with placebo. Eligible subjects will be randomized in a 1:1 ratio to receive a single dose of AG-920 or matching placebo into one eye, designated as subject's study eye. The application of one single dose of AG-920 involves two drops 30 seconds apart into the subject's study eye.

The study consists of two visits and a follow-up phone call: one screening visit on Day -2 (Visit 1), one baseline/assessment visit on Day 1 (Visit 2), and one follow-up phone assessment on Day 2-5 (Phone Follow-Up).

Following the screening visit, eligible subjects will return to the clinic on Day 1 to have their study eye randomly assigned (right eye=OD or left eye=OS) and to be randomized to receive the study medication into the study eye. Subjects will undergo a conjunctival pinch procedure, and the pain associated with the pinch will be rated. Dosing of the study medication and conjunctival pinch procedure will be performed by the study staff.

To assess the anesthetic effect of the study medication, all subjects will be pinched at 20, 40, 60 seconds and 5 minutes post dose, defined as after the second drop of the dose application. If the subject feels no pain at 5 minutes, the subject will be considered "anesthetized." Pinching of anesthetized subjects will resume at 10 minutes and pinching will continue every five minutes for up to 30 minutes or until pain resumes. If the subject experiences pain 5 minutes post dose, pinching will be concluded and this subject will be considered to NOT have reached anesthesia.

All subjects who are randomized and who receive the study medication on Day 1 will be followed up with a phone call to on Day 2-5 for safety assessment.

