### 2.9.1 Primary efficacy analysis

The primary efficacy endpoint for this study is the proportion of subjects with anesthetic response defined as no pain at 5 minutes post application of the dose. The definition of the primary efficacy endpoint is given in Section 2.6.1. The non-parametric Cochran-Mantel-Haenszel (CMH) test with adjustment for study eye side will be used to examine the difference in proportion of subjects with anesthetic response at 5 minutes post dose between the active treatment group and placebo group. If the proportion of subjects (expressed as a percentage) is higher in the AG-920 group and the  $P$  value is statistically significant ( $P \leq 0.05$ ), then superiority of AG-920 over placebo will be claimed.

Between-group difference and its 95% confidence interval (CI) in the proportion of subjects with anesthetic response (yes=1) vs. non-response (no=0) will be calculated using a two-way analysis of variance (ANOVA) model with treatment (the effect of interest) and study eye side as the effects. The study-eye-side effect is used as a blocking factor in the model to control the potential treatment differences among the study eye sides.

The primary efficacy analysis will be performed for the ITT population, which will include all of the randomized subjects who received the complete application of one study dose (i.e., two drops). The analysis model adjusts for the effect of the study eye side. The study-eye-side by treatment interaction will be examined through the summary descriptive statistics of subjects with anesthetic response for each study eye side.

Prior to the determination of the primary efficacy variable, handling of missing values that occur prior to or at 5 minutes post dose is described in Section 2.8.

The primary efficacy endpoint will also be analyzed for the PP population as well as for subgroups of the ITT population, such as male vs. female, Caucasian vs. Non-Caucasian, age groups, and iris color dark brown vs. other colors.

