### **2.9.3 Safety analysis**

#### Treatment Exposure

Frequencies of exposure to the study medication will be calculated based on the number of drops the subject has received over the course of the study. Frequencies of exposure will be categorized as the following: 1 drop and 2 drops. Frequencies of exposure will be summarized by treatment for the safety population defined in Section 3.1, as well as for each gender group.

Compliance rates will be calculated by dividing the number of drops received by the number of drops that should have been given during the application of dose. Compliance rates will be summarized.

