### Intention-to-treat (ITT) Population

This population is defined as all subjects who are randomized to treatment and have received at least one dose (two drops) of the study medication. The ITT population is the primary population for efficacy evaluation in this study. Treatment identification is defined in the ITT population by treatment assignment. The ITT population will be identified and finalized before the database is locked and the study is unmasked.

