### **3.7 Protocol Deviations and Violations**

A summary of protocol deviation and violations will be provided for ITT population (Table 1.5.1). Subjects who are randomized to receive double-masked treatment in the study and included in the ITT population, but do not have two drops dosed and/or post-dose status of pinch pain assessment will be listed for subjects randomized (Listing 4).

Subjects who are included in the ITT population, but not included in the PP population due to either protocol violations or other reasons will be listed for all subjects excluded from the PP population (Listing 5).

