### **4.2 Treatment Compliance**

The compliance rate during treatment will be summarized by treatment group and demographic parameters for the safety and ITT populations (Tables 1.5.2 and 1.5.3).

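### The primary ITT set requires both drops, so a randomized subject who stops after one drop leaves the primary comparison, and other SAP text does not fit that rule; the effect is probably small and its direction undocumented

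*SAP*

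**What the plan says.** **ITT set.** Three places agree. SAP 2.9.1 uses "all of the randomized subjects who received the complete application of one study dose (i.e., two drops"). SAP 3.1 has "all subjects who are randomized to treatment and have received at least one dose (two drops) of the study medication". Protocol 9.3 has "The ITT population will include all randomized subjects who have received at least one dose (2 drops) of study medication". PP is a subset of ITT in both documents.

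**Partial dosing.** SAP 2.9.3 allows for it: "Frequencies of exposure will be categorized as the following: 1 drop and 2 drops". It also says "Compliance rates will be calculated by dividing the number of drops received by the number of drops that should have been given", and SAP 4.2 adds "The compliance rate during treatment will be summarized by treatment group and demographic parameters for the safety and ITT populations". SAP 3.7 (Listing 4) covers randomized subjects who are "included in the ITT population, but do not have two drops dosed and/or post-dose status of pinch pain assessment".

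**Timing and missing pinches.** SAP 2.2 times the pinches at 20, 40 and 60 seconds and "5 minutes post dose, defined as after the second drop of the dose application". SAP 2.8 and protocol 9.5 fill missing Day 1 values in ITT by LOCF. The last line of SAP 2.8 leaves anything still incomplete as missing. PP uses observed data only (SAP 3.1, protocol 9.5).

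**Safety set.** Protocol 9.3 requires both drops; SAP 3.1 requires one.

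**The concern.** An intention-to-treat set should not lose randomized subjects because of what happens once treatment has started. Here a subject who receives the first drop and refuses or cannot have the second is removed from the primary comparison. Protocol 1.2 names stinging or burning on instillation as an expected risk and gives no rate by arm, so the reason for leaving could differ between arms.

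The rest of the SAP does not fit the definition. Part of Listing 4 describes ITT subjects who cannot exist, and one compliance table cannot vary. A programmer would have to guess which text governs.

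There is a related gap at the endpoint. If the 5-minute pinch is missing or invalid, LOCF can turn a no-pain answer at 60 seconds or earlier into a primary success that was never observed at 5 minutes. A subject with no post-dose pinch stays missing and drops out of the test.

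**Working it through.** **1. The plan's own figure.** Inputs from SAP 2.5: 60 per arm, 15% against 40%, two-sided 0.05, chi-square without continuity correction. The pooled rate is 0.275.
- SE under the null = sqrt(2 x 0.275 x 0.725 / 60) = 0.0815.
- SE under the alternative = sqrt(0.15 x 0.85/60 + 0.40 x 0.60/60) = 0.0783.
- z = (0.25 - 1.96 x 0.0815) / 0.0783 = 1.15, so power is 87.6%. The stated 88% reproduces and is not in dispute.

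**2. Tracing a one-drop subject through the text.**
- SAP safety set: in. Protocol safety set: out.
- ITT: out under all three definitions. PP: out, as a subset of ITT.
- Listing 4: described as an ITT member, which the definition rules out. The other half of that listing, ITT subjects with no post-dose pinch, remains possible.
- ITT compliance: drops received / drops due = 2/2 = 100% for every member.
- If ITT were widened and nothing else changed: no second drop, so no planned pinch time, nothing for LOCF to carry, and the last line of SAP 2.8 leaves the subject missing.

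**3. Effect of losing one-drop subjects.** The documents give no rate of partial dosing, so the counts are assumptions. Take full data at the design rates, 24/60 against 9/60, and lose two subjects from one arm. P is a single-stratum CMH, Pearson x (N-1)/N, which approximates the eye-stratified test.

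| Case | AG-920 | Placebo | Difference (points) | P |
|---|---|---|---|---|
| Full data | 24/60 | 9/60 | 25.0 | 0.0023 |
| Two lost on AG-920, neither would respond | 24/58 | 9/60 | 26.4 | 0.0015 |
| one would respond | 23/58 | 9/60 | 24.7 | 0.0027 |
| both would respond | 22/58 | 9/60 | 22.9 | 0.0048 |
| Two lost on placebo, neither would respond | 24/60 | 9/58 | 24.5 | 0.0032 |
| one would respond | 24/60 | 8/58 | 26.2 | 0.0014 |
| both would respond | 24/60 | 7/58 | 27.9 | 0.0006 |

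The shift runs from 22.9 - 25.0 = -2.1 to 27.9 - 25.0 = +2.9 points. Every case stays significant.

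**4. How many carried-forward successes would matter.** Against 9/60, reversing AG-920 successes gives:
- five reversed, 19/60: CMH P = 0.0316;
- six reversed, 18/60: CMH P = 0.0501, but Pearson (the protocol 9.4.6 test) P = 0.0491;
- seven reversed, 17/60: CMH P = 0.0775, Pearson P = 0.0763.

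So six reversals are needed under the SAP's test and seven under the protocol's.

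**5. Is non-response better than LOCF?** Let a fraction m be missing at random in each arm, with true 5-minute rates p1, p0 and 60-second rates q1, q0.
- Error in the difference, non-response: -m x (p1 - p0) = -0.05 x 0.25 = -1.25 points at an assumed m = 5%.
- Error, LOCF: m x [(q1 - q0) - (p1 - p0)]. This is smaller than 1.25 points in size whenever q1 - q0 lies between 0 and 50 points.
- Missing in one arm only, non-response: -0.05 x 0.40 = -2.0 points on AG-920, or +0.05 x 0.15 = +0.75 points on placebo.

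Neither rule is uniformly better, and non-response is not always conservative.

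**The case against.** The strongest reply is that this rarely happens and is already covered. Staff give both drops 30 seconds apart, subjects must tolerate an artificial tear at screening (protocol 4.1 and 6.3), and protocol 9.5 expects minimal missing data. A one-drop row in an exposure table is routine and does not show that such exits are expected. The ITT set is fixed before unmasking, and both documents state the same imputation rule. All of this stands, and it limits the size. It does not remove the conflict between the ITT definition and SAP 3.7, or between the two safety sets. Tolerating a tear product also does not rule out stinging from the study drop.

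Three stronger readings are tempting, and the documents do not support them.
- *That no planned analysis shows the result without imputed responses.* The PP analysis of the primary endpoint (SAP 2.9.1, Table 2.1.2) uses observed data. Protocol 9.3 waives it only if PP equals ITT and nothing is missing. It also removes major violators, so it is not an observed-case analysis of ITT. Table 1.6.1 and Listing 6 additionally show what was imputed. What can be said is that no readable passage plans an ITT analysis with missing counted as non-response. The table list is redacted, so even that is limited to readable text.
- *That one-drop subjects would be missing from the safety tables.* The SAP set that those tables use includes them, and exposure has a row for them. What remains is a wording conflict with the protocol.
- *That the rules favour AG-920, or that LOCF is an error.* No rate by arm is given, and the working shows shifts in both directions.

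**Conclusion.** The point holds as a matter of definition and consistency. The ITT set excludes randomized, dosed subjects for a reason arising after dosing began; SAP 3.7 and 4.2 do not fit that definition; and the safety-set wording differs between the documents. It should be corrected while the trial is still masked, but it does not threaten the primary result at the design rates. Two lost subjects move the difference by about 2 to 3 points at most, and six or seven reversed successes are needed to lose significance. These sizes rest on assumed counts, on the 40% and 15% design rates, and on a single-stratum approximation. A single subject would matter only for a result already near the 0.05 boundary. The absence of a non-response analysis is a gap in supportive evidence; it is not a fault in the primary method.

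**What to change.** (a) In protocol 9.3 and SAP 2.9.1 and 3.1, define ITT as all randomized subjects given any drop, analysed as randomized. Reconcile SAP 3.7 with it. SAP 4.2 then becomes informative for ITT.

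(b) In SAP 2.8 and protocol 9.5, count a subject with no pinch to carry forward, including a one-drop subject, as a non-responder. Without this, (a) does not bring one-drop subjects back into the test.

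(c) Use at least one drop for the safety set in both documents.

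(d) Optional: keep LOCF primary and add a supportive ITT analysis in which a missing or invalid 5-minute pinch counts as non-response.

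**Cost.** Items (a) to (c) are wording. The any-drop set fits protocol 10.3, which provides for data capture once IMP is administered; protocol 10.4 refers to receiving a dose and should be aligned. Scoring one-drop subjects as non-responders, compared with excluding them, lowers the difference slightly if they are on AG-920 (24/58 becomes 24/60, 26.4 to 25.0 points against 9/60). It raises the difference slightly if they are on placebo (9/58 becomes 9/60, 24.5 to 25.0 points against 24/60). Item (d) is one extra table and costs no power as a supportive analysis. If it were made primary, exact power under the single-stratum CMH would fall from 87.8% to 86.9%, 85.4% or 82.6% at an assumed 2%, 5% or 10% missing per arm.

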### 2.9.2 Secondary efficacy analysis

The secondary efficacy endpoints include 1) the onset of anesthetic effect defined as the time to no pain by conjunctival pinch within 5 minutes post application of the dose; and, 2) the duration of anesthetic effect defined as the time from the onset of anesthetic effect to the time point when pinch pain resumes. Secondary efficacy endpoints will be analyzed for the ITT population and PP population.

Prior to the determination of the secondary efficacy variables, handling of missing values that occur prior to or at 5 minutes post dose or after 5 minutes post dose on Day 1 is described in Section 2.8.

#### Onset of anesthetic effects

The secondary endpoint of the onset of anesthetic effect in minutes from time of dose application completion to no pain within 5 minutes post dose is defined in Section 2.6.2. This endpoint will be compared for between-group differences, using a 2-way ANOVA model with treatment (the effect of interest) and study eye side as the effects. The study-eye-side effect is used as a blocking factor in the model to control the potential treatment differences among the study eye sides. For the accuracy and appropriateness of the analysis, those subjects who are censored on (or not achieving) the onset of anesthetic effect will be excluded from statistical analysis.

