2 OBJECTIVES AND ENDPOINTS

Primary Objective

To evaluate anesthetic efficacy of AG-920

Secondary Objectives

To evaluate how long it takes one dose of AG-920 to anesthetize the eye

To evaluate how long one dose of AG-920 anesthetizes the eye

To evaluate the safety and tolerability of AG-920

Primary Endpoints

The proportion of subjects with no pain at 5 minutes.

Secondary Endpoints

Mean time to no pain score (onset)

Mean duration of anesthetic effect

Visual acuity, biomicroscopy, AEs, TEAEs, SAEs, withdrawals due to TEAEs

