### **2.6.1 Primary efficacy measure**

The primary efficacy endpoint for this study is the proportion of subjects with anesthetic response defined as no pain at 5 minutes post application of the dose. Pain is assessed using conjunctival pinch procedure. Dosing of the study medication and conjunctival pinch procedure will be performed by the study staff.

To assess the anesthetic effect of the study medication, all subjects will be pinched at 20, 40, 60 seconds and 5 minutes post dose application. If the subject feels no pain at 5 minutes, the subject will be considered "anesthetized." Pinching of anesthetized subjects will resume at 10 minutes and pinching will continue every five minutes for up to 30 minutes or until pain resumes. If the subject experiences pain 5 minutes post dose application, pinching will be concluded and this subject will be considered to NOT have reached anesthesia.

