### **2.6.2 Secondary efficacy measure**

The secondary efficacy endpoints include the following:

- Time in minutes to no pain within 5 minutes post application of the dose defined as post the 2nd drop of the dose. Once a subject achieves no pain or anesthetic effect, the time to the onset of anesthetic effect will be calculated as the time interval in number of minutes between the time of dose application completion and the time point when the first observation of no pain is recorded. All timepoints post dose will be converted to minutes so the 20, 40 and 60 second timepoints will be 0.33, 0.67 and 1.0 minutes, respectively. For those subjects who drop out after dose application without achieving anesthesia or who do not achieve the anesthetic effect within 5 minutes post dose, the time to the anesthetic effect will be considered being censored at the last assessment of pinch test or at 5 minutes (censored time point), whichever occurs earlier.
- Duration in minutes from the onset of anesthetic effect to the time point when pinch pain resumes. For those subjects who have achieved an anesthetic effect post dose, the duration of anesthetic effect is calculated by subtracting the anesthetic effect onset time from the time of the first observation of pinch pain return. For those subjects who did not achieve an anesthetic effect post dose, this duration is not applicable and will be set to missing.

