##### **4.5.2 Results of secondary efficacy analyses**

Descriptive and inferential statistics of the anesthetic response onset in minutes post dose will be presented in Table 2.3.1 for the ITT population and in Table 2.3.2 for the PP population.

Descriptive and inferential statistics of the anesthetic response duration in minutes from the onset to pinch pain return will be presented in Table 2.4.1 for the ITT population and in Table 2.4.2 for the PP population.

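### The onset test leaves out every subject who never became pain-free by 5 minutes, so its ITT-labelled p-value does not compare the randomized groups

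*SAP*

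**What the plan says.** SAP 2.6.2 measures onset from completion of the dose to "the time point when the first observation of no pain is recorded", with pinches at 20, 40 and 60 seconds and 5 minutes. For a subject with no onset in that window, "the time to the anesthetic effect will be considered being censored at the last assessment of pinch test or at 5 minutes", whichever is earlier. This is a time-to-event definition with a censoring rule.

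The analysis in SAP 2.9.2 (Onset of anesthetic effects) does not use that rule. It fits a two-way ANOVA with treatment and study eye side, and "those subjects who are censored on (or not achieving) the onset of anesthetic effect will be excluded from statistical analysis".

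The result is presented as a full-population comparison. SAP 2.9.2 says "Secondary efficacy endpoints will be analyzed for the ITT population and PP population", and SAP 4.5.2 says "Descriptive and inferential statistics of the anesthetic response onset in minutes post dose will be presented in Table 2.3.1 for the ITT population". The ITT definition in SAP 3.1 requires randomization and a complete two-drop dose. It sets no condition on outcome.

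**The concern.** Whether a subject has an onset is observed after randomization, and raising that proportion is the purpose of the drug. Keeping only subjects with an onset therefore selects differently in the two arms, and randomization no longer makes the kept subjects comparable. The p-value would be read as a treatment effect on onset, which is a stated secondary objective. It ignores how many more subjects become numb on AG-920, and its direction depends on how onset times are distributed, which the documents do not give. A drug that adds responders at the later pinches could be reported as significantly slower than placebo without having slowed anyone.

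**Working it through.** **Inputs from the SAP.** Section 2.5: 60 per group, 15% placebo response, 25-point difference (so 40% on AG-920), two-sided 0.05, chi-square without continuity correction, 88% power. Section 2.6.2: onset times 0.33, 0.67, 1 and 5 minutes. Section 2.9.2: ANOVA on treatment and eye side. Onset rates and onset-time patterns are not given, so those below are assumptions.

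**The plan's own figure.** With mean rate 0.275, power = Φ{[0.25√60 − 1.96√(2 × 0.275 × 0.725)] / √(0.15 × 0.85 + 0.40 × 0.60)} = Φ{(1.936 − 1.238) / 0.606} = Φ(1.15) = 87.6%. The stated 88% reproduces.

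**Subjects dropped** = 60 × (1 − onset rate) per arm.

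- Onset rates equal to the planning rates: placebo 60 × 0.85 = 51, AG-920 60 × 0.60 = 36. Total 87 of 120 = 72.5%, leaving 9 against 24. The planning rates are for no pain *at* 5 minutes. A first pain-free pinch *by* 5 minutes is at least as common, so at these rates 87 is the most that would be dropped under the first-pinch definition.
- Four independent pinches at those rates: onset rates 1 − 0.85⁴ = 47.8% and 1 − 0.60⁴ = 87.0%. Dropped: 60 × 0.522 = 31.3 and 60 × 0.1296 = 7.8, total about 39 of 120 = 33%.

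The loss is unequal between arms in both cases.

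**What the ANOVA then shows.** Simulation with 60 per arm, eye side random 1:1, and 4,000 trials in each of ten scenarios. Onset shapes over the four times: early (0.5, 0.2, 0.15, 0.15), even (0.25 each), late (0.1, 0.2, 0.3, 0.4), with means 1.20, 1.75 and 2.47 min. The planned test was fitted as least squares of onset on treatment and eye among subjects with an onset. Mean onset among those kept is Σpₖtₖ / Σpₖ. For example, with all placebo responders at 20 s and the extra 25 points spread evenly, the AG-920 mean is (0.15 × 0.33 + 0.25 × 1.75) / 0.40 = 1.22 min. The last three rows use 15% against 40% with an onset.

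| Assumed pattern (early / even / late shape) | Mean onset, placebo vs AG-920 (min) | ANOVA p<0.05 for AG-920 | ANOVA p<0.05 for placebo |
|---|---|---|---|
| Independent pinches (one scenario) | 1.47 vs 1.00 | 28.0% | 0.07% |
| Same shape in both arms | equal: 1.20 / 1.75 / 2.47 | 3.2 / 3.1 / 2.5% | 0.8 / 1.1 / 2.0% |
| Half of placebo-type responders at 20 s, the rest by shape | 0.76 / 1.04 / 1.40 vs 1.04 / 1.48 / 2.07 | 1.2 / 0.5 / 0.4% | 1.5 / 4.5 / 11.3% |
| All placebo responders at 20 s, extra 25 points by shape (extreme) | 0.33 vs 0.87 / 1.22 / 1.67 | 0 / 0 / 0% | 2.8 / 13.7 / 40.9% |

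On the same data, a log-rank test on all 120 subjects, stratified by eye, favours AG-920 in 84.6-87.3% of trials in the last three rows and 99.9% in the first. It favoured placebo in 0 of 40,000 trials, as expected when every scenario gives AG-920 the higher onset rate.

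**A further check.** In a separate simulation (a two-sample t-test among achievers standing in for the ANOVA, even placebo shape), all 25 added points first become pain-free at 5 minutes. The AG-920 mean is (0.15 × 1.75 + 0.25 × 5) / 0.40 = 3.78 min against 1.75 min, and AG-920 is significantly slower in 69% of runs although no subject is made slower.

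**The case against.** The strongest reply is that the protocol lists mean onset time as the endpoint, and a mean exists only for subjects who have an onset. On that view the ANOVA answers how fast, while a log-rank test mostly repeats the primary question of whether. The log-rank power of about 85-87% is close to the primary test's 88% because both detect 15% against 40%. Two further assumed cases support this. With 40% achieving in both arms, AG-920 early and placebo late, the ANOVA detects faster onset in about 60% of trials and the log-rank test in 7%. With placebo 15% early and AG-920 40% late, the log-rank test still favours AG-920 in 83%, although AG-920 achievers are slower. This stands as a limit on the remedy. It does not turn a p-value among achievers into a comparison of randomized groups.

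Other points:

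- Who counts as not achieving is not fully settled. SAP 2.6.2 uses the first pain-free pinch, so a subject pain-free at 40 seconds but in pain at 5 minutes keeps an onset time. SAP 2.6.1 says of a subject in pain at 5 minutes that "this subject will be considered to NOT have reached anesthesia". Either reading selects on outcome; only the number dropped changes.
- Independence of repeated pinches in one subject has no support in the documents. The 33% figure and the first table row depend on it.
- The table and figure lists are redacted, so it can only be said that the visible text contains no all-subject onset analysis. LOCF (SAP 2.8) fills missing pinches, and the non-parametric option (SAP 2.9) addresses non-normality. Neither brings non-achievers back.
- The exclusion is openly pre-specified, the endpoint is secondary, and no visible text attaches a claim to its p-value. That limits the weight of the point.

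**Conclusion.** The point holds. As written, the onset p-value compares subjects selected by a post-randomization outcome, and the ITT label does not describe it. This follows from the text and needs no assumption about onset patterns. The size does: between about 39 and 87 of 120 subjects are dropped under the two assumptions used. The ANOVA may favour AG-920 (28% of trials with independent pinches), show almost nothing (2.5-3.2% when shapes match) or favour placebo (1.5-11.3% with half of placebo responders at 20 seconds, up to 40.9% in the extreme pattern). It should be corrected before unmasking. The primary analysis and the superiority claim in SAP 2.9.1 do not depend on it.

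**What to change.** In SAP 2.9.2, compare time to first pain-free pinch in all ITT subjects. Apply the censoring rule already in SAP 2.6.2, show Kaplan-Meier curves, and test with a log-rank test stratified by study eye, with a stated method for ties at the four discrete times. State that an onset at 5 minutes counts as an event before censoring at 5 minutes.

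An alternative is an eye-stratified rank test placing non-achievers last. It favoured AG-920 in 74.9-86.6% of trials in the nine 15%-against-40% scenarios and 99.7% with independent pinches.

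Do not use a mean restricted to 5 minutes, because it scores onset at 5 minutes the same as no onset. In the further check above, the placebo value is 0.15 × 1.75 + 0.85 × 5 = 4.51 min and the AG-920 value is 0.15 × 1.75 + 0.25 × 5 + 0.60 × 5 = 4.51 min, despite 25 points more responders.

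Keep the protocol's mean onset time as a descriptive statistic labelled achievers only, with the number excluded per arm and no between-group p-value. Settle which definition of not achieving applies. Also say how LOCF in SAP 2.8 and censoring at the last pinch in SAP 2.6.2 fit together for early dropouts; few are expected.

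The cost is SAP wording and one standard procedure, with no new data. The price is overlap: the new p-value partly repeats the primary comparison and says little about speed alone, so the achiever means and the curves must carry that part.
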